8.5. Time-to-Resolution Definition

In order to derive the time-to-resolution, overlapping or contiguous AESI within a specific category will be collapsed into what will be termed "clustered" AESI. For example, if a subject (without pre-treatment AE) experienced an AE from 01 January to 05 January, another AE (with different PT but within same category) from 06 January to 11 January, and the same AE from 10 January to 12 January, these will be collapsed into one clustered AESI from 01 January (onset date) to 12 January (resolution date). Table 11 summarizes key derivation steps for each type of clustered select AEs.

Time-to-resolution of AESI (any grade) for a specific category is defined as the longest time from onset to complete resolution or improvement to the grade at baseline among all AESI clusters in this category experienced by patients. Events which worsened into Grade 5 events (death) or have a resolution date equal to the date of death are considered unresolved. If a clustered AESI is considered to be unresolved, the resolution date will be censored to the last known alive date. Improvement to the grade at baseline implies that all different AE events in the clustered AESI should at least have improved to the corresponding (that is, with same preferred term) baseline grade (or improve to lower grade). Time-to-resolution is defined only for subjects who experienced at least one AESI in the specific category.

The time-to-resolution of AESI (Grade 3-5) for a specific category is defined similarly with an onset date corresponding to a Grade 3-5 AESI.

Time-to-resolution of drug-related AESI (any grade or Grade 3-5) is defined similarly but restricted to drug-related AESI.

Time-to-resolution for a specific subcategory is defined similarly but restricted to events of this subcategory.

Table 11: Derivation of Clustered AESI

Type of clustered select AE	Derivation	
Any grade	Collapse any on-treatment AESI from the same category	
Drug-related of any grade	Collapse any on-treatment drug-related AESI from the same category	
Grade 3-5	Collapse any on-treatment AESI from the same category. Resolution will be based on the onset date of the earliest Grade 3-5 records (clusters with only Grade 1-2 should not be selected)	
Drug-related of Grade 3-5	Collapse any on-treatment drug-related AESI from the same category. Resolution will be based on the onset date of the earliest Grade 3-5 record (clusters with only Grade 1-2 should not be selected)	

Abbreviations: AE=adverse event; AESI=adverse event of special interest.

The algorithm for collapsing selected AE records is using the following conventions. For each patient and specified category, the corresponding AE records will be collapsed when:

- Multiple AE records have the same onset date.
- The onset date of an event record is either the same day or 1 day later than the resolution date of a preceding event record (contiguous events).
- The onset date of an event record is after the onset date and prior to or on the resolution date of a preceding event record (overlapping events).

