6.5.2.6. Adverse Events of Special Interest

Incidence

Adverse event of special interest (AESI) will be summarized:

- Summary of AESI with the number and percentage of patients reporting AESI, serious AESI, grade ≥ 3 AESI, AESI leading to study drug discontinuation, interruption and dose reduction, and AESI with outcome of deaths.
- Summary of AESI by worst CTC grade (grade 1, 2, 3, 4, 5, any grade, Grade ≥ 3) presented by category or subcategory / PT

A by-patient listing of AESI will also be provided.

Time to Onset

Time-to-onset of selected AESI (e.g. hyperphosphatemia) will be graphically displayed using the Kaplan-Meier technique.

- Time-to-onset of any grade AESI
- Time-to-onset of Grade >3 AESI

The derivation of time-to-onset of AESI is detailed in Section 8.4.

Time to Resolution

Time-to-resolution of selected AESI (e.g. hyperphosphatemia) will be summarized.

• Time-to-resolution of Grade ≥3 AESI

The following summary statistics will be reported: percentage of subjects who experienced the specific events, percentage of subjects with resolution of the AESI (clustered), median, 1st quartile and 2nd quartile of time-to-resolution along with 95% CI (derived from Kaplan-Meier estimation) and ranges.

Time-to-resolution of Grade ≥3 AESI (e.g. hyperphosphatemia) will be graphically displayed using the Kaplan-Meier technique.

Time-to-resolution analyses are restricted to patients who experienced the specific events. Collapsing selected AE and derivation of time-to-resolution of AESI is detailed in Section 8.5.

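### SAP 8.5 does not give an unresolved or fatal cluster priority, so a patient with a longer, earlier resolved cluster can enter the AESI time-to-resolution analysis as resolved

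*SAP*

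**What the plan says.** SAP 8.5 first merges AESI records in a category into clusters. Records merge only if they share an onset date, overlap, or are contiguous; the contiguity condition is "The onset date of an event record is either the same day or 1 day later than the resolution date of a preceding event record". Episodes further apart remain separate clusters, so a patient can have several.

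Each patient then gets one value per category: "the longest time from onset to complete resolution or improvement to the grade at baseline among all AESI clusters in this category".

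Two sentences deal with events that do not resolve. The first classifies deaths: "Events which worsened into Grade 5 events (death) or have a resolution date equal to the date of death are considered unresolved". The second gives such a cluster an end point, and so a finite length: "If a clustered AESI is considered to be unresolved, the resolution date will be censored to the last known alive date".

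The version that reaches a planned table is the severe one: "The time-to-resolution of AESI (Grade 3-5) for a specific category is defined similarly with an onset date corresponding to a Grade 3-5 AESI". Table 11 moves the onset to the earliest Grade 3-5 record and drops clusters with only Grade 1-2 records. It does not say how resolved and unresolved clusters in one patient are combined.

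SAP 6.5.2.6 plans, for Grade 3 or higher events in selected AESI (hyperphosphatemia is the example), "percentage of subjects with resolution of the AESI (clustered), median, 1st quartile and 2nd quartile of time-to-resolution along with 95% CI", together with a Kaplan-Meier plot. It does not say whether every cluster must have resolved for a patient to count.

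**The concern.** The censoring sentence works on the cluster, but the analysis has one record per patient. An unresolved cluster receives a finite length, from onset to last known alive date, and is then compared on length with the resolved clusters. If a resolved cluster is longer, it supplies the patient's value, and nothing in 8.5, Table 11 or 6.5.2.6 turns that record into a censored one.

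That is wrong for a maximum. If one component is censored, the maximum is only bounded below, and recording an event claims knowledge that the data do not contain. It also contradicts the rule that fatal events are unresolved: the fatal cluster is so classified, but the patient is not.

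At stake is the credibility of a reversibility summary. The error goes one way, towards more resolution. It falls on patients whose last event was fatal or began shortly before death or data cut-off.

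**Working it through.** **Reproducing the SAP's own example.** Records on 1-5, 6-11 and 10-12 January, put through the three collapsing conditions, give one cluster from 1 to 12 January, as SAP 8.5 states.

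**A structural consequence.** A cluster that is still open absorbs every later record. An unresolved cluster is therefore always the patient's last one, and misclassification needs at least one separate, earlier, resolved cluster.

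**Why the record should be censored.** Let T = max(T1, ..., Tk) over k clusters, with the last observed only to time c. The data say T ≥ max(t1, ..., t(k-1), c). T equals the longest resolved time only if the last cluster would have resolved within that time, which is unknown (and, for a fatal cluster, false).

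**Two test patients** (assumed; duration = end day minus onset day). Cluster 1 runs from day 10 to day 40 and resolves.

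| Second cluster | Literal rule: longest of all clusters | Alternative reading: longest of the resolved clusters | Correct record |
|---|---|---|---|
| Day 100 to death on day 110 | 30 days, resolved | 30 days, resolved | 30 days, censored |
| Day 100, unresolved, last known alive day 160 | 60 days, censored | 30 days, resolved | 60 days, censored |

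Both readings misclassify the fatal case. The alternative reading also misclassifies the second patient.

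**How likely is one misclassification?** Assume exponential resolution times with a 14-day median and one earlier resolved cluster of length X. An unresolved cluster observed for C days is outranked with probability P(X > C) = exp(-C·ln2/14):

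| C (days) | 3 | 5 | 14 | 30 | 90 |
|---|---|---|---|---|---|
| Probability | 86% | 78% | 50% | 23% | 1% |

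The length of the unresolved cluster decides the matter.

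**Patient-level simulation.** All inputs are assumed. Gaps between clusters and durations are exponential. The unresolved cluster ends at the end of observation, as with death or cut-off.

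| Follow-up (days) | Mean gap (days) | Mean duration (days) | Unresolved patients scored resolved | % resolved, literal rule | % resolved, every cluster required |
|---|---|---|---|---|---|
| 180 | 45 | 14 | 68.0% | 92.4 | 76.2 |
| 180 | 45 | 30 | 58.7% | 83.5 | 60.1 |
| 360 | 60 | 14 | 79.6% | 96.2 | 81.3 |
| 360 | 60 | 30 | 74.7% | 91.7 | 67.1 |

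Check on row 1: 100 - 76.2 = 23.8% have an unresolved cluster, and 76.2 + 23.8 × 0.680 = 92.4.

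**Moving the last known alive date.** With that date 180 days after the end of observation, the share scored resolved falls to 0.0% (inputs of row 1) and 0.2% (inputs of row 4).

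A second model uses variable treatment time (exponential, mean 180 days, minimum 28, plus 30 days), a mean gap of 60 days and a 14-day median duration. It gives about 50% when last known alive equals the end of adverse event follow-up. This falls to about 12% or 6.5% when last contact averages 90 or 180 days later. With the first date assumption but a mean gap of 180 days, it gives about 29%.

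**The case against.** The strongest reply is that the SAP never says a patient inherits the status of the longest cluster. A careful programmer could recognise that a maximum with a censored component is itself censored. On that view a sentence is missing, and no wrong rule is stated. It is fair that the text is silent. But the censoring sentence is about a clustered AESI, not a patient, and the literal reading and the obvious alternative both score the fatal case as resolved. The correct result needs a step that is not written down.

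A reader might infer that fatal AESI vanish from the report. They do not. SAP 6.5.2.6 tabulates AESI with a fatal outcome, AESI by worst grade including Grade 5, and a by-patient listing. SAP 6.5.2.1 lists all deaths, and 6.5.2.2 summarises adverse events leading to death.

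A reader might also take half or more as the expected misclassification. The documents do not support that. Adverse event collection stops 30 days after the last dose (Protocol 8.1.1), while survival contact continues every 12 weeks (Protocol 3.2.6). A non-fatal unresolved cluster is therefore often carried well past the event, becomes the longest, and is correctly censored. The planned output covers only Grade 3 or higher events, and Protocol 1.2.2 describes hyperphosphatemia as mostly Grade 1-2, so repeat qualifying clusters may be few. Both arguments stand and limit the size.

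Finally, it is tempting to say that the longest cluster inflates the median and that the first cluster should replace it. That is a choice of estimand. The longest cluster is a conservative summary that the SAP adopts openly. A first-cluster score would again record the fatal test patient as resolved at 30 days.

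**Conclusion.** The point holds in limited form. As written, SAP 8.5 can enter a patient with an unresolved or fatal cluster into the time-to-resolution Kaplan-Meier analysis as resolved, against its own treatment of fatal events. For the percentage with resolution, the same follows only if that percentage uses the same patient-level score; 6.5.2.6 gives no other rule.

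The size cannot be computed from the documents, which give no recurrence rates, durations or contact dates. The assumed scenarios run from about 0% to 50-80% of patients with an unresolved cluster. The upper end needs frequent separate clusters and a last known alive date at the end of observation. That date condition suits deaths during adverse event follow-up and patients with no later contact before cut-off, so the bias falls mainly there.

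The output is descriptive. No primary endpoint, error rate or stopping rule is touched. The correction is worth making because the status is wrong in exactly the fatal cases and costs little to put right.

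**What to change.** Add to SAP 8.5, for the any-grade, Grade 3-5 and drug-related versions alike: a patient is resolved for a category only if every qualifying cluster in that category resolved; if any is unresolved or fatal, the patient is censored at the longest of that patient's observed cluster durations. In 6.5.2.6, state that such a patient counts as not resolved in the percentage with resolution. The fatal test patient then becomes 30 days, censored, in place of 30 days, resolved.

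Keep the longest-cluster definition; no first-cluster median is needed.

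The cost is a sentence in 8.5, the matching statement in 6.5.2.6, a small programming change, and a percentage resolved that may be slightly less favourable.

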8.6. Other Data Handling Rules

Missing data will not be imputed in listings. The listings will only present the data recorded on the original CRF.

If an AE has a completely missing onset date, then the AE will be considered a TEAE. A medication with a completely missing start date is considered a prior medication. A medication with a completely missing stop date is considered a concomitant medication.

If an adverse event or a medication has a partial missing start date or stop date, the following rules will be used to determine whether it is a TEAE, or a prior or concomitant medication.

 Table 12.
 Partial Date Imputation Rule for TEAE or Medication

Partial Missing Start or	Derived Start Date	Imputed Stop Date
Stop Date		
Missing month and day,	January 1 of that year or first dose	December 31 of that
and the year is present	date if the year is the same as the	year
	year of first dose date	
Missing day, but year and	First day of that month or first	Last day of that month
month are present	dose date if the year and month are	
	the same as the year and month of	
	first dose date	
Missing month, but year	Missing month derived as January	Missing month imputed
and day are present	or same as first dose month if the	as December
	year is same as the year of first	
	dose.	

A date with missing year will be considered as completely missing date, no imputation rule will be applied.

The rule in Table 12 is also used for determining the cycle of adverse event and concomitant medication. The derived date is used for determining TEAEs, the cycle of adverse event and concomitant medication.

For medical history, pre-study surgery, prior radiotherapy, and prior systemic anticancer therapies, a partial missing start date will be imputed as below:

- Missing year no imputation, date left missing
- Missing day and month January 1 will be assigned to the missing fields.
- Missing month only Treat day as missing and replace both month and day with January 1.
- Missing day only Assign the first day of the month to the missing day.

Note: additional rules for prior systemic anticancer therapies may apply as they pertain to checking for protocol violations

For medical history, pre-study surgery, prior radiotherapy, and prior systemic anticancer therapies, a partially missing stop dates will be imputed as below:

- Missing year no imputation, date left missing
- Month is missing and year is prior to year of first dose of study drug- impute 'December'.
- Month is missing and year is the same as the year of the first dose of study drug impute same month as in first dose date of study drug.

• Day is missing - impute 'last day of that month'. If results in a date ≥ the date of the first dose of study drug impute day as the day prior to date of first dose of study drug.

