8.2. Post-Baseline Period

To allow differentiation as to which study period an Adverse Event occurred, three categories are defined based upon onset date. Adverse Events that had onset dates prior to the first dose of study drug are considered "prior". Adverse events with onset dates on or after the first dose of study drug and within 30 days following the last dose of study drug are considered "on-treatment" or equivalently "treatment emergent". Events with onset dates more than 30 days after the last dose of study drug are considered as "post-treatment". No "subtracting rule" will be applied when an AE occurs both pre-treatment and post-treatment with the same preferred term and grade. AE summary tables will be based on on-treatment AEs only. Adverse events with onset dates prior to the first dose of study drug as well as those after the last dose of study drug +30 days will be identified in the data listings.

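### SAP Table 12 can date an on-treatment AE with a missing month before first dose, and no AE start-date rule checks for a stop date before first dose

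*SAP*

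**What the plan says.** SAP 8.6, Table 12, gives three start-date rules for AEs and medications with partial dates.

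- Row 1, month and day missing: "January 1 of that year or first dose" date when the year is the first-dose year.
- Row 2, day missing: "First day of that month or first" dose date when year and month match those of first dose.
- Row 3, month missing, day and year present: "Missing month derived as January", "or same as first dose month if the" year is that of first dose. Only the month is supplied.

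A wholly missing onset has its own default: "If an AE has a completely missing onset date, then the AE will be considered a TEAE".

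The derived date has consequences: "The derived date is used for determining TEAEs, the cycle of adverse event and concomitant medication". SAP 8.2 classes onsets before first dose as prior and states: "AE summary tables will be based on on-treatment AEs only". SAP 6.5.2.2 keeps every AE in listings.

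For medical history and prior therapy, the start-date rule in SAP 8.6 for a missing month is different: "Treat day as missing and replace both month and day with January 1".

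**The concern.** Rows 1 and 2 move the start to the first dose date when the known parts match it. Row 3 does not. It builds a date from the first-dose month and a day that may belong to another month, and that date can fall before dosing. An AE with more date information can then be excluded, while the same AE with less information is included. This runs against the inclusive default that the SAP sets for a wholly missing onset.

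The second gap works in the other direction. Protocol 8.1.1 collects AEs from consent, and SAP Table 2 allows up to 28 days between consent and first dose. None of the AE start-date rules compares the result with the stop date, so an event that was over before dosing can be tabulated as treatment-emergent.

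TEAE status decides whether an AE enters the summary tables, and safety is a secondary objective. Cohorts are small: one patient is 1/55 = 1.8% of Cohort 1 or 2 at full size, 1/28 = 3.6% of Cohort 4 and 1/24 = 4.2% of Cohort 3.

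**Working it through.** The SAP gives no figure on this point, so there is none to reproduce. The rules can be followed by hand and then enumerated.

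**Examples**

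- First dose 20 March 2020; AE truly starts 15 April 2020; month not recorded. Row 3 gives 15 March 2020: prior, not in the tables. With the day also missing, row 1 gives 20 March 2020: TEAE.
- First dose 20 March 2020; screening AE starts on an unknown day of March and stops 12 March. Row 2 gives a start of 20 March: TEAE, starting 8 days after its own stop.
- First dose 20 June 2021; AE runs 25 to 30 May 2021; onset month missing. Row 3 gives 25 June 2021: TEAE, although the event ended 21 days before first dose.

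**How often row 3 dates an AE before first dose**

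Let *d* be the recorded day, *f* the first-dose day and *m* the days in the month. For an AE in the first-dose year, the derived date precedes first dose when *d* < *f*.

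- For a given *f*, with *d* uniform: (*f* - 1)/*m*. With *m* = 31 this is 0/31 = 0% for day 1, 9/31 = 29% for day 10, 14/31 = 45% for day 15, 24/31 = 77% for day 25 and 30/31 = 97% for day 31.
- With *d* and *f* both uniform: (*m* - 1)/(2*m*) = 27/56 = 48.2%, 29/60 = 48.3% and 30/62 = 48.4% for *m* = 28, 30 and 31.

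The 48% is too high for true on-treatment AEs, because an onset after dosing but within the first-dose month cannot have *d* < *f*. It also ignores AEs in a later calendar year. Row 3 dates those to January of that year, which is after first dose.

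An enumeration over all 365 first-dose dates in a year allows for both. It takes AEs truly on or after first dose and sets an impossible day to the last day of the month. The onset distributions are assumptions, not taken from the documents.

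| Assumed onset after first dose | First-dose-year AEs misdated | All month-missing AEs misdated |
|---|---|---|
| Uniform, 15 days | 22% | 21% |
| Uniform, 30 days | 45% | 43% |
| Uniform, 90 days | 45% | 40% |
| Uniform, 365 days | 44% | 22% |
| Exponential, mean 14 days | 30% | 29% |
| Exponential, mean 60 days | 42% | 35% |
| Exponential, mean 120 days | 43% | 30% |

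**How often a screening AE becomes a TEAE**

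For onsets spread evenly over the 28 days before dosing, the share is 44% with the month missing, 52% with the day missing and 96% with both missing. The stop date plays no part in any of these.

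**Number of AEs**

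The documents do not give it. As an illustration only, assume 10 AEs per patient, of which 0.1-1% have a missing month and a known day.

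- About 75 patients (Cohorts 1-3 stop at stage 1, Cohort 4 treats 28: 19 + 19 + 9 + 28): 750 AEs, 0.75-7.5 with the pattern; times 21-43% gives 0.2-3.2 misdated.
- 168 patients (the ceiling, 55 + 55 + 24 + 34): 1,680 AEs, 1.7-16.8 with the pattern; times 21-43% gives 0.4-7.2 misdated.

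**The case against.** A reader might infer that about half of all month-missing AEs disappear. The documents do not support that. The figure near 48% needs uniform, independent days and covers only AEs in the first-dose year; later-year AEs are never dated before first dose. Nor do the AEs vanish. All are listed, SAP 8.2 identifies those outside the on-treatment window in the listings, and SAP 8.6 keeps recorded dates there. The laboratory shift tables in SAP 6.5.3 use laboratory results, so raised phosphorus, for example, is still summarised. SAP 6.5.2.2 also counts an AE that worsens after first dose, which could recover some events.

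A day without a month is an obvious query target. Protocol 8.1.1 requires onset and resolution dates, and Protocol 11.6 and 11.7.2 provide for queries and source verification. Few such records should reach analysis.

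The contrast with medical history is not clean either. The day is discarded there for start dates, but the stop-date rules in SAP 8.6 fill a missing month without discarding the day. Finally, counting a pre-dose AE as a TEAE over-reports toxicity, which is the conservative direction.

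All of this limits the size of the problem. None of it makes row 3 give the right date, and none explains why a known stop date before first dose should be ignored.

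**Conclusion.** Both errors follow directly from the rules as written. Row 3 can move an on-treatment AE out of the summary tables. Every AE start-date rule, including the one for wholly missing onset, can admit an AE known to have ended before dosing. The classification of a given record is deterministic and does not depend on any assumed percentage.

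Under the onset distributions above, roughly 20-45% of month-missing on-treatment AEs would be misdated. The share depends heavily on the first-dose day, and AEs in a later calendar year are not affected. The absolute number is unknown and probably very small; the counts shown rest on assumed AE and missing-month rates. No primary endpoint or stage 1 decision is affected. This is a minor correction, worth making because it is cheap.

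**What to change.** Two changes to SAP 8.6.

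1. In Table 12 row 3, when the year is the first-dose year, do not let the derived start fall before the first dose date. Either treat the day as missing and apply row 1, or keep the day and use the later of the derived date and the first dose date. TEAE status is the same under both. The second distorts cycle and time to onset less, but only modestly, since the two dates differ by at most 31 - 1 = 30 days. If the day is kept, add a rule for impossible dates, such as day 31 in a 30-day month.
2. For all rows and for wholly missing onset: if the known or latest possible stop date is before first dose, class the AE as pre-treatment, and never derive a start later than the stop date. Table 12 already has a column for imputing partial stop dates.

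The first change leaves no on-treatment AE in the first-dose year dated before first dose. The second leaves no AE known to have ended before dosing counted as a TEAE.

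The cost is two sentences and a small change to the date program. The downside is that some AEs with an unknown month and no informative stop date, including screening events, will be counted as TEAEs and assigned to Cycle 1. Before the stop-date check, the share of month-missing screening AEs counted this way rises from 44% to 96%. That is the conservative direction and matches rows 1 and 2.
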